### 3.5 Supportive Care

3.5.1 [Appendix II](#) details required supportive care and management guidelines for immune-related toxicity

### 3.6 Duration of Agent-specific treatment

In the absence of treatment delays due to adverse event(s), treatment may continue until one of the following criteria applies:

- Extraordinary Medical Circumstances: If at any time the constraints of this protocol are detrimental to the patient's health, protocol treatment should be discontinued. In this event submit forms according to the instructions in the MATCH Forms Packet.
- Patient withdraws consent.
- Patient experiences unacceptable toxicity.
- Non-protocol therapies are administered. Patients who require palliative radiation therapy may be considered to remain on study after discussion and approval by the subprotocol chair(s). Treatment with nivolumab should be halted during radiation therapy.

- Any dosing interruption lasting >6 weeks, with the following exceptions:  
Dosing interruptions >6 weeks that occur for non-drug-related reasons may be allowed if approved by the Investigator. Prior to re-initiating treatment in a subject with a dosing interruption lasting >6 weeks, the Principal Investigator must be consulted. Tumor assessments should continue as per protocol even if dosing is interrupted.
- Disease progression
- Please see Section [3.7](#) for details regarding treatment past progression

### 3.7 Treatment Past Progression

A minority of subjects treated with immunotherapy may derive clinical benefit either delayed responses, stable disease, or increased overall survival despite initial evidence of progressive disease (PD) with nivolumab or combination treatment.

Patients may be permitted to continue treatment beyond initial RECIST 1.1-defined PD occurring during 24 weeks as long as they meet the following criteria:

- No more than 4 new lesions total sum of the longest diameter (SHORT diameter for LN) cannot exceed 40% of the initial sum including new lesions
- Patients must be clinically stable with no change in performance status due to disease progression
- No indication for immediate alternative treatment
- Patient (assessed by the investigator) is showing clinical benefit and tolerates study drug. The assessment of clinical benefit should take into account whether the subject is clinically stable or deteriorating and likely or unlikely to receive further benefit from continued treatment.
- The time of progression is noted from the first assessment that exceeds standard criteria
- New lesions are considered measurable at the time of initial progression if the longest diameter is at least 10 mm (except for pathological lymph nodes, which must have a short axis of at least 15 mm). Any new lesion considered non-measurable at the time of initial progression may become measurable and therefore included in the tumor burden measurement if the longest diameter increases to at least 10 mm (except for pathological lymph nodes, which must have an increase in short axis to at least 15 mm).

### 3.8 Duration of Follow-Up

Refer to the MATCH Master Protocol for specifics on the duration of follow-up.

Rev. 12/16  
Rev. 3/17,  
Add13

#### 4. Study Parameters

##### 4.1 Therapeutic Parameters for Nivolumab Treatment

**NOTE:** In addition to the study parameters listed in the MATCH Master Protocol, the below parameters must also be performed for patients receiving nivolumab treatment.

**NOTE:** All assessments required prior to registration to treatment should be done ≤ 4 weeks prior to registration to Steps 1, 3, 5, 7, excluding the radiologic evaluation and electrocardiogram (ECG).

Test/Assessment	Prior to Registration to Treatment	Treatment		End of Treatment	Follow Up F
		Every Cycle, prior to treatment	Every 2 Cycles		
H&P, Weight, Vital signs A	X	X I			X
Performance status	X	X I			X
CBC w/diff, plts B	X	X I			X
Serum chemistry B	X	X I			X
Thyroid function testing [TSH (with reflex to free T4 ± free T3 if abnormal)]	X	X			X
Radiologic evaluation D	X		X D		X F
β-HCG C	X				
Toxicity Assessment G		X		X	X F
ECG	X	X H			
ECHO	X H				
Tumor biopsy and blood sample for MATCH Master Protocol E			X	X	
Research Blood (See Section 6) J		X J		X J	
Archival tumor block or 20 (at least 5 micron thick) unstained slides, if available	X K				

- A. History and physical, including vital signs and weight at the start of each cycle (up to 3 days before start of new cycle). A contraceptive, menstrual, and sexual history be obtained with each H&P for all women of childbearing potential and sexually active men.
- B. Albumin, alkaline phosphatase, total bilirubin, bicarbonate, BUN, calcium, creatinine, glucose, phosphorus, potassium, SGOT[AST], SGPT[ALT], sodium, magnesium, TSH (with reflexive Free T4 ± Free T3 if abnormal), serum tumor markers (prior to each cycle, not each dose). For eligibility purposes, participants with creatinine levels above eligibility, Cockcroft-Gault will be used to calculate creatinine clearance. CBC w/diff, platelets and serum chemistries should be performed on cycle 1, day 1 (or up to 7 days prior), and at the start of each subsequent dose (up to 3 days

before start of next dose) while tumor markers are performed prior to day 1 of a cycle (up to 3 days before). CBC with differential will be performed more frequently in patients with grade 4 neutropenia or thrombocytopenia until resolution to  $\leq$  grade 3. CBC and serum chemistries are only required in follow-up until values return to pre-treatment levels or until progressive disease.

- C. Blood pregnancy test (women of childbearing potential) required prior to beginning treatment.
- D. Disease measurements are repeated every 2 cycles for the first 26 cycles, and every 3 cycles thereafter until PD or start of another MATCH treatment step. The baseline evaluation should be performed as closely as possible to the beginning of treatment and never more than 6 weeks before registration to treatment step. For multiple myeloma patients, please refer to Section 6.4 of the MATCH Master Protocol for additional information on myeloma response criteria and the required disease assessments. Documentation (radiologic) must be provided for patients removed from study for progressive disease.
- E. Additional blood specimens and/or biopsies are to be submitted from consenting patients per Section 9.3.2 of the MATCH Master Protocol. Submit at the following time points, as applicable:
  - Blood specimens are to be submitted at the end of Cycle 2 (prior to start of Cycle 3 treatment). If patient progresses or treatment is discontinued prior to Cycle 3, collect the blood at that time instead. On-treatment kits for blood sample collections will be automatically shipped to sites upon registration to the treatment step.
  - Screening biopsies for additional aMOI assessments after registration to appropriate screening step, if applicable (Step 2 or Step 4).
  - At end of all MATCH study treatments, blood specimens and/or research biopsy after consent and registration to Step 8

Please refer to Section 4 of the MATCH Master Protocol to determine whether the patient proceeds to the next screening step or to follow-up (with a potential end of treatment biopsy for research purposes on Step 8). Samples are to be submitted as outlined in Section 9 of the MATCH Master Protocol. To order Step 2/4 Screening or Step 8 kits, complete the EAY131 Collection and Shipping Kit Order Form (See Appendix XII of the MATCH Master Protocol) and fax to [contact].

- F. Every 3 months if patient is  $<$  2 years from study entry, and every 6 months for year 3. Toxicity assessments and radiologic evaluations are not required to be done during Follow Up if progression has been previously reported; however if an adverse event occurs post treatment that meets the SAE reporting requirements, it still must be reported via CTEP-AERS, even if progression has occurred.
- G. Site personnel should evaluate for toxicity and discuss treatment compliance with the patient in order to ensure the medication is taken correctly; this evaluation may be conducted by telephone or in person. The Toxicity Assessment is not required prior to Cycle 1, but is required every subsequent cycle.
- H. Evaluate cardiac function including EKG and ECHO for any patients with a history of CHF or at risk because of underlying cardiovascular disease or exposure to cardiotoxic drugs, as clinically indicated. For patients with evidence of CHF, MI, cardiomyopathy, or myositis cardiac evaluation including lab tests and cardiology consultations as clinically indicated including EKG, CPK, troponin, ECHO.
- I. For Cycle 1, if the following tests/assessments occurred within 7 days of Day 1, they do not need to be repeated at this timepoint: H&P, Weight, Vital Signs; Performance Status; CBC w/diff, plts; Serum chemistry; Concomitant Medications.
- J. From consenting patients, collection prior to start of treatment and end of cycle 2 (prior to start of cycle 3) and End of treatment.
- K. MANDATORY: Submit per EAY131 Master Protocol (Section 9.3 and Section 9.4) prior to or within 8 weeks following registration to EAY131-Z1D.

Rev. Add13 **5. Drug Formulation and Procurement**

This information has been prepared by the ECOG-ACRIN Pharmacy and Nursing Committees.

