## 2. Selection of Patients

Each of the criteria in the checklist that follows must be met, along with the eligibility in the MATCH Master Protocol, in order for a patient to be considered eligible for this study. Use the checklist to confirm a patient's eligibility. For each patient, this checklist must be photocopied, completed and maintained in the patient's chart.

**In calculating days of tests and measurements, the day a test or measurement is done is considered Day 0. Therefore, if a test is done on a Monday, the Monday four weeks later would be considered Day 28.**

ECOG-ACRIN Patient No. \_\_\_\_\_

Patient's Initials (L, F, M) \_\_\_\_\_

Physician Signature and Date \_\_\_\_\_

**NOTE:** Policy does not allow for the issuance of waivers to any protocol specified criteria ([http://ctep.cancer.gov/protocolDevelopment/policies\\_deviations.htm](http://ctep.cancer.gov/protocolDevelopment/policies_deviations.htm)). Therefore, all eligibility criteria listed in Section 2 must be met, without exception. The registration of individuals who do not meet all criteria listed in Section 2 can result in the participant being censored from the analysis of the study, and the citation of a major protocol violation during an audit. All questions regarding clarification of eligibility criteria must be directed to the Group's Executive Officer ([[contact]](mailto:[contact])) or the Group's Regulatory Officer ([[contact]](mailto:[contact])).

**NOTE:** Institutions may use the eligibility checklist as source documentation if it has been reviewed, signed, and dated prior to registration/randomization by the treating physician.

**NOTE:** All patients must have signed the relevant treatment consent form

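### The only scheduled pregnancy test can be 28 days old at registration and older at first dose, while contraception is required only from 7 days before treatment

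*Protocol*

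**What the plan says.** Protocol Section 4.1 sets a common window for everything required before registration: these assessments "should be done ≤ 4 weeks prior to registration to Steps 1, 3, 5, 7, excluding the radiologic evaluation and electrocardiogram (ECG"). Section 2 fixes the day count: "if a test is done on a Monday, the Monday four weeks later would be considered Day 28".

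In the Section 4.1 table the beta-HCG row has a single mark, in the pre-registration column. Footnote C to that row reads: "Blood pregnancy test (women of childbearing potential) required prior to beginning treatment".

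Other Cycle 1 assessments are tied to the first dose. Footnote B states: "CBC w/diff, platelets and serum chemistries should be performed on cycle 1, day 1 (or up to 7 days prior"). Footnote I waives a Cycle 1 repeat for items done within 7 days of Day 1, and its list is "H&P, Weight, Vital Signs; Performance Status; CBC w/diff, plts; Serum chemistry; Concomitant Medications". Beta-HCG does not appear there.

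Sections 2.1.14 and 5.1.9 have women of childbearing potential use contraception from one week before treatment until 5 months after the last dose. Footnote A adds a non-laboratory check: "A contraceptive, menstrual, and sexual history be obtained with each H&P for all women of childbearing potential".

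The table does not stand alone: "In addition to the study parameters listed in the MATCH Master Protocol, the below parameters must also be performed". Section 2.1.1 likewise brings in Master Protocol eligibility.

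**The concern.** The two windows do not meet. The pregnancy test counts back from registration and may be four weeks old by then. Contraception counts back from the first dose and covers only the last week. A conception after a negative test and before that week is possible under the stated calendar, and no later test is scheduled to detect it.

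The protocol treats fetal exposure as serious. It requires contraception for 5 months after the last dose, and Section 3.2.1 makes a pregnancy on treatment reportable within 24 hours. Yet the first dose may rest on a negative result that predates conception. The blood count and chemistry, by contrast, are held to 7 days before Cycle 1 Day 1.

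**Working it through.** **Inputs**

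- t = days from the beta-HCG test to registration. The Section 4.1 NOTE allows up to 4 weeks, and the plan's own figure reproduces as 4 × 7 = 28 days under the Section 2 counting rule. So t runs from 0 to 28.
- L = days from registration to first dose. No value or cap is given. Section 5 (Availability) bars starter supplies and allows a drug request only after enrolment and assignment, with the drug then shipped to the site. L is therefore above 0 for a site holding no supply. The values 0, 3, 7 and 14 below are assumptions.
- Required contraception begins 7 days before first dose (Sections 2.1.14 and 5.1.9).
- Repeat tests scheduled in this subprotocol: none.

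**Formulas**

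- Age of the test at first dose = t + L
- Days after the test with neither required contraception nor a further scheduled test = max(0, t + L − 7)

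**Oldest permitted test (t = 28)**

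| L (assumed) | Age at first dose | Days without required contraception |
|---|---|---|
| 0 | 28 + 0 = 28 | 28 − 7 = 21 |
| 3 | 28 + 3 = 31 | 31 − 7 = 24 |
| 7 | 28 + 7 = 35 | 35 − 7 = 28 |
| 14 | 28 + 14 = 42 | 42 − 7 = 35 |

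**Earlier use of the window**

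| t | Gap at L = 0 | Gap at L = 3 |
|---|---|---|
| 0 | 0 | 0 |
| 7 | 0 | 3 |
| 14 | 7 | 10 |
| 21 | 14 | 17 |

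There is no gap when t + L ≤ 7. These are calendar counts of what the text permits, not probabilities of exposure. The number of women of childbearing potential is not given.

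**What falls inside the gap.** The footnote A history accompanies the physical examination. Its timing is "History and physical, including vital signs and weight at the start of each cycle (up to 3 days before start of new cycle"), or within 7 days of Day 1 for Cycle 1 under footnote I. It is therefore a required, dated check close to dosing, but no test is attached to it.

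**The case against.** The strongest objection is that this is a supplement. The Master Protocol's study parameters and most of its Section 3.1 eligibility criteria also apply, and that document was not available. It may hold a shorter pregnancy-test window, a repeat test or a limit on the time from registration to first dose. This stands: the text shows a gap in the subprotocol's own windows, not that one exists in the trial as run.

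Second, nothing here is contradictory. A four-week ceiling before registration and contraception from one week before dosing are separate rules, and both can be obeyed. The 7-day window proposed below is borrowed from other assessments. That is also true, and it is why this is a point about a design choice. The borrowing is reasonable because the protocol already uses that window for Cycle 1 blood work.

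Third, the footnote A history could bring out a missed period or unprotected intercourse. It deserves weight, but it can miss an early, unrecognised pregnancy.

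Fourth, footnote C could be read as asking for a test near the first dose. It states no window, however, and a 28-day-old result satisfies its words.

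Last, the figures are worst cases. Only the 21-day figure at L = 0 avoids an assumed delay after registration, and it needs a test on the last permitted day with dosing on the day of registration. The tables show how quickly the gap shrinks with later testing.

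**Conclusion.** The point holds for the windows this subprotocol states. The single scheduled beta-HCG test may be 28 days old at registration and 28 + L days old at first dose. In the worst case, 21 + L days follow it without required contraception or another scheduled test: 21 days at L = 0, and 24, 28 and 35 days at assumed L of 3, 7 and 14. The footnote A history is the only remaining check scheduled here.

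The conclusion depends on the Master Protocol not being tighter, so confidence is medium. This is a participant-safety matter and changes no endpoint, sample size or error rate. It should be corrected because the correction is small and does no harm if the Master Protocol already covers it.

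**What to change.** Change footnote C alone, to this effect:

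> Women of childbearing potential must have a negative blood pregnancy test within 7 days before Cycle 1 Day 1, with the result available before the first dose. If the pre-registration test is older than that, repeat it. Any stricter Master Protocol window applies.

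This forces the test used for dosing to be at most 7 days old, so the gap becomes 0 days. Footnotes B and I should stay as they are, because adding beta-HCG to them could imply testing before every dose.

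The cost is one sentence and, for a patient tested early, one repeat assay. It can use blood already drawn for the count and chemistry within 7 days of Cycle 1 Day 1, but the result must be back before dosing. A very early conception can still be missed, so the edit removes the calendar gap but not all risk. If the Master Protocol already has a tighter rule, the edit only brings footnote C into line with it.

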**Availability**

NO STARTER SUPPLIES MAY BE ORDERED. Subjects must be enrolled and assigned to the treatment subprotocol prior to submitting the clinical drug request to PMB.

Drug Ordering: NCI supplied agents may be requested by eligible participating Investigators (or their authorized designee) at each participating institution. Pharmaceutical Management Branch (PMB) policy requires that drug be shipped directly to the institution where the patient is to be treated. PMB does not permit the transfer of agents between institutions (unless prior approval from PMB is obtained – see general information) The CTEP-assigned protocol number must be used for ordering all CTEP-supplied investigational agents. The eligible participating investigators at each participating institution must be registered with CTEP, DCTD through an annual submission of FDA Form 1572 (Statement of Investigator), NCI Biosketch, Agent Shipment Form, and Financial Disclosure Form (FDF). If there are several participating investigators at one institution, CTEP-supplied investigational agents for the study should be ordered under the name of one lead investigator at that institution.

Submit agent requests through the PMB Online Agent Order Processing (OAOP) application (<https://ctepcore.nci.nih.gov/OAOP>). Access to OAOP requires the establishment of a CTEP Identity and Access Management (IAM) account (<https://ctepcore.nci.nih.gov/iam/>) and the maintenance of an “active” account status, a “current” password, and an active person registration status.

**NCI Supplied Agent(s) – General Information**

**Questions about drug orders, transfers, returns, or accountability should be addressed to the PMB by calling [contact] Monday through Friday between 8:30 AM and 4:30 PM Eastern Time or email [[contact]](mailto:[contact]) anytime.**

**Drug Returns:** All undispensed drug supplies should be returned to the PMB. When it is necessary to return study drug (e.g., sealed bottles remaining when PMB sends a stock recovery letter), investigators should return the study drug to the PMB using the NCI Return Agent Form available on the NCI home page (<http://ctep.cancer.gov>).

**Drug Accountability:** The investigator, or a responsible party designated by the investigator, must maintain a careful record of the receipt, disposition, and return of agent received from the PMB using the NCI Investigational Agent Accountability Record Form available on the NCI home page (<http://ctep.cancer.gov>). Maintain separate NCI Investigational Agent Accountability Records for each agent, strength, formulation and ordering investigator.

Rev. 12/16

Rev. 3/17

**Investigator Brochure Availability:** The current versions of the IBs for PMB-supplied agents will be accessible to site investigators and research staff through the PMB Online Agent Order Processing (OAOP) application. Access to OAOP requires the establishment of a CTEP Identity and Access Management (IAM) account and the maintenance of an “active” account status, a “current” password, and active person registration status. Questions about IB access may be directed to the PMB IB coordinator at [[contact]](mailto:[contact]).

Rev. 3/17

5.1 Nivolumab (NSC #748726)

5.1.1 Other Names  
BMS-936558, MDX1106

5.1.2 Classification  
Anti-PD-1MAb

5.1.3 Mode of Action  
Nivolumab targets the programmed death-1 (PD-1, cluster of differentiation 279 [CD279]) cell surface membrane receptor. PD-1 is a negative regulatory receptor expressed by activated T and B lymphocytes. Binding of PD-1 to its ligands, programmed death-ligand 1 (PD-L1) and 2 (PD-L2), results in the down-regulation of lymphocyte activation. Nivolumab inhibits the binding of PD-1 to PD-L1 and PD-L2. Inhibition of the interaction between PD-1 and its ligands promotes immune responses and antigen-specific T-cell responses to both foreign antigens as well as self-antigens.

Rev. Add13  
Rev. Add16

5.1.4 Storage and Stability

Storage:

Vials of Nivolumab injection must be stored at 2°-8°C (36°-46°F) and protected from light and freezing. The unopened vials can be stored at room temperature (up to 25°C, 77°F) and room light for up to 48 hours.

If a storage temperature excursion is identified, promptly return Nivolumab to 2°C-8°C and quarantine the supplies. Provide a detailed report of the excursion (including documentation of temperature monitoring and duration of the excursion) to [[contact]](mailto:[contact]) for determination of suitability.

Stability:

Shelf-life surveillance of the intact vials is ongoing. The administration of undiluted and diluted solutions of Nivolumab must be completed within 24 hours of preparation. If not used immediately, the infusion solution may be stored up to 24 hours in a refrigerator at 2°-8°C (36°-46°F) and a maximum of 8 hours of the total 24 hours can be at room temperature (20°-25°C, 68°-77°F) and room light. The maximum 8-hour period under room temperature and room light conditions includes the product administration period.

**CAUTION:** The single-use dosage form contains no antibacterial preservative or bacteriostatic agent. Therefore, it is advised that the product be discarded 8 hours after initial entry.

Rev. Add16

5.1.5 Dose Specifics

Description: Nivolumab Injection is a clear to opalescent, colorless to pale yellow liquid; light (few) particulates may be present. The drug product is a sterile, nonpyrogenic, single-use, isotonic aqueous solution formulated in sodium citrate dihydrate, sodium chloride,

mannitol, diethylenetriaminepentacetic acid (pentetic acid) and polysorbate 80 (Tween® 80), and water for injection. Dilute solutions of hydrochloric acid and/or sodium hydroxide may be used for pH adjustment (pH 5.5-6.5).

Rev. Add13

How Supplied: Nivolumab is supplied by Bristol-Myers Squibb and distributed by the Pharmaceutical Management Branch, CTEP/DCTD/NCI as 100 mg vials (10 mg/mL) with a 0.7mL overfill. It is supplied in 10 mL type I flint glass vials, with fluoropolymer film-laminated rubber stoppers and aluminum seals.

Rev. Add16

